- Death witnessed and instantaneous without new or worsening symptoms;
- Death witnessed within 60 minutes of the onset of new or worsening cardiac symptoms, unless the symptoms suggest an acute myocardial infarction;
- Death witnessed and attributed to an identified arrhythmia, e.g., captured on an electrocardiographic (ECG) recording, witnessed on a monitor, or unwitnessed but found on implantable cardioverter-defibrillator review;
- Death after unsuccessful resuscitation from cardiac arrest;
- Death after successful resuscitation from cardiac arrest and without identification of a non-cardiac etiology (Post-Cardiac Arrest Syndrome); and
- Unwitnessed death without other cause of death (information regarding the participant's clinical status preceding death should be provided, if available).

General considerations for SCD are that a subject seen alive and clinically stable 12-24 hours prior to being found dead without any evidence or information of a specific cause of death should be classified as SCD. Deaths for which there is no information beyond "Patient found

dead at home” may be classified as “death due to other cardiovascular causes” or “undetermined cause of death”¹⁰³. A strategy for dealing with such deaths will be decided on by the Executive Committee prior to study initiation. Cause of death determination will be National Death Index (National Center for Health Statistics); the NDI *Plus* database has been shown to be highly accurate in resolving cause of death¹⁰⁴; an Adjudication Committee may be assembled if deemed necessary by the Executive Committee.

4. All-cause Hospitalization

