The Data Monitoring Committee (DMC) provides interim, independent, and unbiased reviews of the study's ongoing progress. The DMC is composed of clinical and statistical members who have expertise in clinical trials and/or the subject area(s) of the study. These experts are not participants in the trial and have not participated in the planning of the protocol. The Principal Proponent, study Biostatisticians, Clinical Research Pharmacist, and the Director of the CSPCC are *ex officio* (liaison, non-voting) members of the DMC. The DMC meets at least annually to review the progress of the study and monitor participant intake, outcomes, adverse events, serious adverse events, and other issues related to participant safety. At its meetings, the DMC reviews the randomization rates and assess the difference between the actual and the projected rates, as well as the impact of these assessments on overall trial size. If the study enrollment is inadequate, impediments to enrollment will be discussed and the reasons for patient exclusion may be scrutinized and actions may be suggested. The DMC's primary responsibilities are to review safety and the progress of the study and to decide whether or not the study should continue. To help the Committee make its assessment, the Principal Proponent and Study Biostatisticians will provide the DMC with appropriate monitoring data before each meeting. The DMC makes recommendations to the Director, VA CSR&D about whether the study should continue or be stopped.

A member of the Human Rights Committee (HRC) at the Coordinating Center conducts a site visit to at least one participating center during the course of the study to determine if participants' rights and safety are being properly protected. The HRC member may interview study participants during the site visit.

The Adjudication Committee will consist of 3 to 5 members nominated by the Executive Committee and chosen for their clinical and technical expertise. Committee members will establish a standard adjudication procedure. The Committee will periodically review endpoint reports and relevant clinical information and vote as to whether or not reported endpoints satisfy the protocol-defined criteria for cardiovascular or sudden cardiac death.

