1.3.2.3 Sudden Cardiac Death

Sudden cardiac death will include deaths that occur unexpectedly that are not preceded by an acute myocardial infarction. SCD will include the following events²²:

- Death witnessed and instantaneous without new or worsening symptoms;
- Death witnessed within 60 minutes of the onset of new or worsening cardiac symptoms, unless the symptoms suggest an acute myocardial infarction;
- Death witnessed and attributed to an identified arrhythmia, e.g., captured on an electrocardiographic (ECG) recording, witnessed on a monitor, or unwitnessed but found on implantable cardioverter-defibrillator review;
- Death after unsuccessful resuscitation from cardiac arrest;

- Death after successful resuscitation from cardiac arrest and without identification of a non-cardiac etiology (Post-Cardiac Arrest Syndrome); and
- Unwitnessed death without other cause of death (information regarding the participant's clinical status preceding death should be provided, if available).

General considerations for SCD are that a subject seen alive and clinically stable 12-24 hours prior to being found dead without any evidence or information of a specific cause of death should be classified as SCD. Deaths for which there is no information beyond "Patient found dead at home" may be classified as "death due to other cardiovascular causes" or "undetermined cause of death" ²². Cause of death determination will be National Death Index (National Center for Health Statistics); the NDI *Plus* database has been shown to be highly accurate in resolving cause of death ²¹; an Adjudication Committee may be assembled if deemed necessary by the Executive Committee.

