Files documenting all in clinic interrogations will be accessed by the Study Team in a separate and independent transaction from that conducted by the care provider as part of routine clinical practice. These files will be used most importantly as source documentation for exploratory analyses of ICD therapy events including the frequency of ICD therapy, the appropriateness of ICD therapy, the rhythms that trigger ICD therapy and the overall number of shocks experienced by participants with ICDs. These files could also be used for other exploratory analyses focusing on other aspects of ICD function. The data contained within these files may be the result of direct interrogation of the device, or a filtered dataset exported from a larger database used in order to increase the efficiency of data analysis.

Lastly, every effort will be made to interrogate the device upon death. This is standard clinical practice and is often impactful in facilitating determination of the cause of death.

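### The sudden-cardiac-death comparison admits device evidence available mainly in the ICD arm, with no stated masking of death review and no single deciding source

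*Combined protocol and SAP*

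**What the plan says.** Protocol VI.B.3 and SAP 1.3.2.3 give the same list of SCD events. One item covers a death attributed to an identified arrhythmia, including one that was recorded, seen on a monitor, "or unwitnessed but found on implantable cardioverter-defibrillator review". Another is "Unwitnessed death without other cause of death". A further rule covers a clinically stable patient seen alive 12 to 24 hours before being found dead: such a death "without any evidence or information of a specific cause of death should be classified as SCD". Deaths about which nothing is known except that the patient was found dead at home may instead be classed as other cardiovascular or undetermined. For these the protocol adds: "A strategy for dealing with such deaths will be decided on by the Executive Committee prior to study initiation". The SAP does not repeat that sentence.

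On device evidence, Protocol VI.C and SAP 1.3.2.5 state: "Lastly, every effort will be made to interrogate the device upon death". Both add that this often helps to establish the cause.

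On who decides, VI.B.3 and SAP 1.3.2.3 say "Cause of death determination will be National Death Index" and make an Adjudication Committee optional. Protocol XII.B describes that committee as one that will exist, with 3 to 5 members who "vote as to whether or not reported endpoints satisfy the protocol-defined criteria for cardiovascular or sudden cardiac death". The schedule of forms in XI.A includes Form 20, a death review completed by a designated adjudication committee.

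Protocol II.D.1 and SAP 1.2.4.1 present SCD as the test of the ICD's mechanism of action. Protocol XV.C.4(c) and SAP 2.2.7.3 analyse it with the primary-outcome method at a two-sided 0.05 level. Protocol IX.B states that participants and site staff are not blinded.

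**The concern.** A between-arm comparison of a cause-specific outcome needs the same evidence, read in the same way, in both arms. Here one kind of evidence is written into the definition and exists by design in one arm. The rules that send unexplained unwitnessed deaths to SCD are common to both arms, but a device log that could confirm or overturn them is available mainly in the ICD arm.

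The log could act in either direction. A recorded arrhythmia could bring into SCD a death that would otherwise be undetermined or put down to another cause. A log without arrhythmia could persuade a reviewer that an unwitnessed death was not sudden cardiac.

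SCD is the outcome readers will use to interpret the mortality result, since the protocol's rationale (I.C.1) treats it as the only outcome an ICD can prevent. An SCD hazard ratio that mixes a device effect with a difference in evidence could mislead either way.

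**Working it through.** **1. The passages side by side.**
- *Evidence.* The ICD-review item and the interrogation at death presuppose a device. In OMT that means drop-ins, assumed at 2.5% per year (XV.A.2). Ignoring deaths, this is 1 − 0.975^3.6 = 8.7% of OMT patients at 3.6 years and 1 − 0.975^5 = 11.9% at 5 years.
- *Source.* VI.B.3 and SAP 1.3.2.3 (death index decides, committee optional) cannot both stand with XII.B and Form 20 (committee votes on the protocol criteria). SAP 2.2.7.3 points to Table 23, which classifies deaths on the documentation available, and that differs by arm.
- *Masking.* IX.B gives the biostatistician and the Data Monitoring Committee coded arms. XIII.E redacts personal information from adjudication documents. XI.B.2 lets selected members of an events adjudication committee see device reports. None of these withholds arm or device data from death review.
- *Sensitivity analyses.* The modified intention-to-treat analysis (SAP 2.2.4) extends to SCD but changes only the time origin and exclusions, not the classification.

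**2. The plan's own figure.** The documents give no SCD rate, effect size or power, so only the all-cause calculation can be reproduced. The inputs, from XV.A.2, are 15% annual control mortality, hazard ratio 0.75, 2.5% annual drop-in, 1% drop-out in year 1, three-year accrual with 2 to 5 years of follow-up, and 102 pilot patients followed for 5 years. A Markov log-rank calculation gives N = 1,431 with 563 events without loss, and N = 1,455 with 562 events with 1% annual loss. The plan states 1,462 and 565, so the figure is reproduced within 3%. It serves here only to anchor the number of deaths: 0.420 × 731 = 307 in the control arm.

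**3. Illustration of size.** All of the following are assumptions:
- no true effect on SCD, and 307 deaths in each arm;
- 20–50% of deaths labelled SCD, so S = 61 to 154 per arm (the top of the range follows the statement in I.B.1 that half of heart-failure deaths are sudden);
- a share u = 0.2 to 0.4 of those resting on the unwitnessed default;
- device data changing the class of a number equal to a fraction r = 0.1 to 0.5 of that share, in the ICD arm only.

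Apparent ratio: 1 − u·r if deaths move out of SCD, 1 + u·r if the same number move in. With SE = √(1/S + 1/(S·ratio)) and z = ln(ratio)/SE, the two-sided rejection rate is Φ(−1.96 − z) + 1 − Φ(1.96 − z).

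| S per arm | u | r | Out: ratio | Rejection | In: ratio | Rejection |
|---|---|---|---|---|---|---|
| 61 | 0.2 | 0.10 | 0.98 | 5.1% | 1.02 | 5.1% |
| 107 | 0.4 | 0.25 | 0.90 | 11.7% | 1.10 | 11.0% |
| 107 | 0.4 | 0.50 | 0.80 | 33.8% | 1.20 | 28.7% |
| 154 | 0.4 | 0.50 | 0.80 | 45.4% | 1.20 | 38.5% |

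The nominal rate is 5%. In the second row (S = 0.35 × 307 = 107), SE = √(1/107 + 1/96.7) = 0.140 and z = ln 0.90 / 0.140 = −0.75.

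**4. Masking of a true effect.** With an assumed true SCD hazard ratio of 0.70 and 107 control-arm SCDs, adding 20% to the ICD-arm count gives 0.70 × 1.2 = 0.84. Power falls from 66% to 23%.

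These figures assume a usable log for every relevant ICD-arm death and none in OMT. XII.J promises interrogation at death only where feasible, and drop-ins carry devices, so the real shift would be smaller for the same u and r.

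**The case against.** The strongest reply is that the named source, the National Death Index, does not depend on arm. VI.A and XV.C.4(c) repeat that a death-index search will be used to establish cause. XV.C.6 places interrogation at death among descriptive device analyses, and XII.B gives device reports to a separate ICD Events Committee. If index coding alone decides, device data may never reach the SCD outcome. This stands as a condition. The documents do not settle it, however. The SCD criteria turn on who witnessed the death, the time since symptoms began and what the device showed, and nothing explains how index codes would supply those facts.

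Second, the ICD-review item largely overlaps the default: an unwitnessed death with a logged arrhythmia and no other cause is SCD already. The item changes a class mainly where another cause was suspected or nothing is known beyond a death at home. Nor does any written rule say that a log without arrhythmia removes a death from SCD. The outward shift is a reviewer's possible inference. Both points stand, and they are why neither size nor sign can be stated.

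Third, the committee is to set its own standard procedure, which could include masking, and IX.B favours decisions without breaking the treatment code where feasible. Neither says that death review is masked.

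A reader might infer that unwitnessed deaths default to SCD only in the OMT arm, or that the test is biased by a known amount in the ICD's favour. The documents do not support that. The default is written for both arms, drop-ins have devices, and the quoted item by itself adds SCDs in the ICD arm, which works against the device.

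**Conclusion.** The point holds as a risk of differential misclassification, not as a demonstrated bias. The evidence admitted for SCD differs by arm, the trial is open label, masking of death review is not stated, and the deciding source is contradictory. Size and sign are unknown. The ranges of 0.80–0.98 and 1.02–1.20 illustrate what the assumed inputs would do and are not estimates.

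All-cause mortality is unaffected. The objectives and analysis sections class SCD as exploratory, although III.A lists it with the secondary objectives and SAP Table 27 labels it secondary. The matter should be settled before deaths are adjudicated because it concerns the trial's only test of mechanism and the repair is cheap. It does not threaten the main conclusion.

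**What to change.** 1. Make Protocol VI.B.3 and SAP 1.3.2.3 agree with Protocol XII.B and Form 20 on one source that decides cause of death. State in the SAP the rule adopted for deaths known only as found dead at home.
2. If the committee decides, have it classify every death on Form 20 from packets masked to arm and implant status, using only sources available in both arms, before any device data are shown. Record the device-informed classification afterwards as a separate field.
3. In Protocol XV.C.4(c) and SAP 2.2.7.3, report the between-arm SCD hazard ratio both without and with device data. Pre-specify the device-free version at least as a sensitivity analysis.

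The cost is wording in both documents, redaction of packets and one extra analysis. If the committee is at present only optional, it must also be convened. Redaction may not hide every trace of an implant. The device-free version may count some non-arrhythmic ICD-arm deaths as SCD and so dilute a true effect toward 1, which is why both versions should be shown.

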- 4) Able and willing to provide informed consent to participate in this study

As evaluation of above inclusion criteria, the ejection fractions must be measured by angiography, radionuclide scanning, or echocardiography, and MI's must be documented and defined according to the consensus document of the Joint European Society of Cardiology/American College of Cardiology Committee for the Redefinition of Myocardial

Infarction Ejection fraction must be measured within 6 months of consenting to be considered eligible for entry. This study will allow the recruitment of inpatients.

B. Exclusion Criteria

All patients satisfying the inclusion criteria will be excluded for any of the following criteria ⁶⁸:

- 1) Enrolled in or planning to enroll in a conflicting trial
- 2) Receiving a bi-ventricular ICD device
- 3) New York Heart Association class IV heart failure
- 4) Cardiogenic shock or symptomatic hypotension while in stable baseline rhythm,
- 5) Coronary artery bypass graft (CABG) or percutaneous transluminal coronary angioplasty (PTCA) within the past 3 months
- 6) An MI within the past 40 days
- 7) Clinical symptoms or findings that would make them a candidate for coronary revascularization
- 8) Irreversible brain damage from pre-existing cerebral disease
- 9) Any disease other than cardiac disease (e.g. cancer, uremia, liver failure), associated with a likelihood of survival less than 1 year
- 10) Circumstance that would prevent completion of the trial and follow-up activities, including medical condition

Regarding co-enrollment in CSP#592 and another trial: in order both study chairs must concur on the dual-enrollment. Both chairs must agree that the co-enrollment does not adversely effect the rights or well-being of the participant, and by either the sponsor (CSPCO) or by one or more of the studies. It is the responsibility of the Principal Investigator or Local Site Investigator

to determine if it is appropriate for a participant to be in more than one study concurrently. This may require, contacting the Principal Investigator of the other study to determine appropriateness. Where practicable, the LSI is encouraged to discuss with the Study Chair and the Executive Committee.

C. Inclusion of Women and Minorities

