Hospitalization information will be captured by participant self-report and medical record review. Self-report is valid and reliable, especially with inpatient care and recall periods less than one year¹⁰⁵; however, hospitalization data will also be collected from VA electronic medical records, and –where feasible– from non-VA providers. The study’s case report forms will contain detailed information about the index hospitalization and will note re-hospitalizations, rehabilitation unit admissions, and long-term care facility admissions. Specifically, the case report forms will record the total number of days of hospitalization. Hospitalizations of any type will be considered: there is no minimum time-frame for hospitalization and both admissions and observations will be considered as countable. In this study, hospitalizations associated with index implantation, re-implantation, or generator changes will not be considered as countable all-cause hospitalizations.

C. Device Data

ICDs monitor and store data on a wide range of parameters including battery and lead function, patient activity, heart rate, frequency of pacing, and most importantly tachyarrhythmia events. The ICD stores extensive data on all tachycardia events that trigger therapy including beat to

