Veterans who satisfy all of the study eligibility criteria, provide written informed consent and complete the necessary baseline assessments will be randomized to one of two treatment strategies: ICD therapy + optimal medical therapy, or optimal medical therapy alone. The treatment assignment will be provided through a web-based randomization platform or over the telephone to the site investigator or coordinator. The treatment allocation ratio for the two treatment regimens will be 1:1 within each stratum; participants will be stratified both by medical center and by Charlson score (Charlson <3 , and Charlson ≥ 3), using a random permuted block scheme with randomly varying block size. Charlson score will be calculated using the method described in Section V. E. The random treatment scheme will be generated by the West Haven CSP Coordinating Center (WH-CSPCC). When a subject is to be randomized, the Study Coordinator or Local Site Investigator will complete the eligibility and baseline forms. If all eligibility criteria are satisfied and informed consent has been obtained, a new randomization will be assigned. This procedure will be tested and validated before enrollment begins.

The WH-CSPCC will review the overall and by-site randomization at least weekly during the enrollment phase of the study, and will be monitoring the randomization transactions with equal or greater frequency. The participant's unique study ID number will be linked in the randomization file to the treatment assignment for each individual. The randomization file data will remain separate from the rest of the study data on the central database.

Randomization will occur in most cases on the same day the patient has completed the necessary portions of the Screening and Baseline assessments and is judged eligible for randomization.

Delay in randomization due to participant or medical circumstances are permitted up to a maximum of 30 days past baseline data collection. When a new participant has been enrolled, his/her electronic medical record will be updated indicating participation in the study. Source documentation for eligibility criteria and randomization will be kept at the site with the participant's study folder.

B. Blinding

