Neither the participant nor the study personnel at the site will be blinded to the treatment assignment. The variable block sizes included in the randomization scheme will be designed to help conceal the next treatment assignment for each site to reduce the chance of selection bias. The Study Biostatistician and the Data Monitoring Committee will operate with a blinded treatment coding (Treatment A versus Treatment B) for the analysis and review of the data, until such time that the DMC requests removal of the blind. As far as is feasible, decision-making within the study will be performed without removing this treatment code.

X. TREATMENT REGIMENS

A. Overview

Eligible patients who consent for the study will be randomized to ICD implant plus optimal medical therapy vs. optimal medical therapy alone. Standards for optimal medical therapy in the study will be defined by current practice guidelines, but will generally comprise medical therapies and lifestyle modifications. Optimal medical therapy will be closely monitored prior to enrollment, in order to be certain Veterans are receiving the best evidence-based care possible. In addition to optimal medical therapy, participants randomized to the ICD arm will have regular consultation with their Device Technician per standard clinical practice.

B. ICD

1. Overview

Participants randomized to the ICD group will be implanted as soon as possible, with a target window of one week or less between randomization and implantation; this time frame is sought in order to minimize the opportunity for SAEs to accrue before study treatment can be delivered, and to create maximum compatibility between the AE collection window on OMT arm (first 30 days post-randomization) and the OMT + ICD arm (30 days post-implantation). ICD therapy will be standardized with respect to rate cut off zone for defibrillation and anti-tachycardic pacing.

2. Device Specifications

This study will enroll patients eligible for standard single- and dual-chamber ICD devices. A dual-chamber device includes a pacing lead in the right atrium, plus a defibrillator lead in the

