An Unanticipated Adverse Device Effect (UADE) means any serious adverse effect on health or safety or any life-threatening problem or death caused by, or associated with, a device, if that effect, problem or death was not previously identified in nature, severity, or degree of incidence in the investigational plan or application, or any other unanticipated serious problem associated with a device that relates to the rights, safety, or welfare of subjects ¹²¹.

All AEs and UADEs with a reasonable causal relationship to the investigative treatment should be considered at least “possibly related.” A definite relationship does not need to be established.

4. Serious Adverse Event (SAE)

An adverse event is considered a Serious Adverse Events (SAE) if, in the view of either the investigator or Sponsor, it results in any of the following outcomes:

- Death
- A life-threatening adverse event
- Inpatient hospitalization or prolongation of existing hospitalization
- A persistent or significant incapacity or substantial disruption of the ability to conduct normal life functions
- A congenital anomaly/birth defect
- Any other condition that, based upon medical judgment, may jeopardize the subject and require medical or surgical treatment to prevent one of the above outcomes.

In particular, this study will not consider any of the following as either an SAE or a hospitalization: index implantation of an ICD device, re-implantation of an ICD after explantation, or generator change.

All serious adverse events are collected, including those related and not related to the study intervention. All serious adverse events with a reasonable causal relationship to the investigative treatment should be considered “related”. All SAEs will be promptly reported by submission of the event into the CSP #592 data capture system within 72 hours of the site investigator being made aware of the event. Email notification of the submission will immediately be relayed by the CSP #592 data capture system to the Study Biostatistician, Clinical Research Pharmacist, and Study Chair. The CSPCRPCC will be responsible for evaluating all serious adverse events for participant safety concerns. Serious adverse events (as defined by CRF 312.32) that are **unanticipated and related to the investigational treatment** are expeditiously reported to the CSPCRPCC Director, CSPCC, CIRB, DMC, and all regulatory agencies.

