2.2.7.2 All-cause Hospitalization

Total hospitalizations, total number of days of hospitalization, and the proportion of participants who require at least one hospitalization during the follow-up period will be summarized by treatment and compared between treatment groups at a 0.05 significance level. No adjustment will be made for multiple testing for tertiary outcomes because they are considered exploratory in nature.

The total hospitalizations and total days of hospitalization will be analyzed using generalized Poisson or negative binomial regression models. If extra zero counts are observed in the above, a zero inflated Poisson model will be used³⁴. In the generalized mixed model, covariates will include site as a random effect, and general health status (Charlson <3 versus ≥ 3 , or as continuous variable) as a fixed effect. Proportion of participants requiring at least one hospitalization will be analyzed using a chi-square test statistic.

Considering informative censoring due to death if there is a treatment effect, we will also summarize hospitalization rate and days of hospitalization based on total active follow-up time. Similar tests as described above will be processed.

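### The all-cause hospitalization count drops every stay associated with ICD implantation, an almost one-sided exclusion that can hide device-related hospital days, and stays in progress at randomization have no rule

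*Combined protocol and SAP*

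**What the plan says.** Protocol VI.B.4 counts hospitalizations of any type: "there is no minimum time-frame for hospitalization and both admissions and observations will be considered as countable". Its one exclusion is that "hospitalizations associated with index implantation, re-implantation, or generator changes will not be considered as countable all-cause hospitalizations".

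Other sections bear on how that exclusion works:

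- **Entry.** Protocol V.A: "This study will allow the recruitment of inpatients".
- **Randomization.** Protocol IX.A: "Randomization will occur in most cases on the same day the patient has completed the necessary portions of the Screening and Baseline assessments".
- **Implantation.** Protocol X.B.1 wants it as soon as possible, "with a target window of one week or less between randomization and implantation".
- **Safety wording.** Protocol XIV.B.4 is narrower: "this study will not consider any of the following as either an SAE or a hospitalization: index implantation of an ICD device". Re-implantation after explant and generator change follow in the same list. It names the procedures, not the stays connected with them.
- **SAP definition.** SAP 1.3.2.4 defines the hospitalization outcome without repeating any exclusion.
- **Analysis.** SAP 2.2.7.2 (and Protocol XV.C.4.b) compares between arms, at 0.05: "Total hospitalizations, total number of days of hospitalization, and the proportion of participants who require at least one hospitalization during the follow-up period". Randomization is given as the time origin for time-to-event analyses only, and neither document says how to treat a stay already under way at randomization.

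**The concern.** At randomization only the ICD arm is assigned an implantation, so the exclusion has almost no counterpart under OMT. The exception is an OMT participant who later receives a device (Protocol XV.A.2 plans for 2.5% a year).

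The exclusion takes out more than the planned procedure. Protocol VII.A lists complications that prolong a hospital stay, and Protocol X.B.5 foresees removal of an infected device followed by re-implantation. Hospital time of this kind is a cost of the device that an all-cause measure should show. An ICD participant already in hospital for another illness when implanted may also lose the illness days.

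Each of these omissions lowers the ICD arm's count. At stake is whether the reported difference in admissions, days or ever-hospitalized proportion reflects the treatment or the counting rule.

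**Working it through.** The plan gives no rate, power or expected difference for hospitalization, so there is no stated figure to reproduce. The check sets the sections side by side and then illustrates size.

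**1. Participant who was an outpatient at randomization (ICD arm).** Let the planned implant stay last *p* days and a complication add *c* days.

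- Protocol VI.B.4 as written: the whole stay is connected with the implantation, so 0 of *p + c* days count.
- Exclusion limited to the planned admission: *c* days count.

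The same holds for an infection stay that includes a re-implantation. This loss does not depend on any rule about stays in progress. Its size cannot be computed, because the plan gives no complication rate or length of stay.

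**2. Participant who was an inpatient at randomization.** Take one patient per arm with the same illness, randomized on hospital day 3 and discharged on day 10, so 10 − 3 = 7 post-randomization days. The ICD patient is implanted during the stay.

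| Reading of the plan | OMT days | ICD days |
|---|---|---|
| Post-randomization days count; exclusion covers the whole stay (VI.B.4 wording) | 7 | 0 |
| Post-randomization days count; exclusion covers the implantation only (XIV.B.4 wording) | 7 | 7, less any days due solely to the implantation |
| Only admissions starting after randomization count | 0 | 0 |

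The plan does not choose among these. Only the first produces the full gap.

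**3. Illustration of size under the first reading, with no true effect.**

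*Inputs from the documents:* 15% annual mortality and 731 per arm (Protocol XV.A and III.E); 102 pilot participants followed 5 years and 1,360 followed uniformly from 2 to 5 years (SAP 2.1). With λ = −ln(0.85) = 0.1625, mean time alive is (1 − e^(−5λ))/λ = 3.42 years for the pilot and, averaged over 2 to 5 years, 2.63 years for the rest. Hence T = (102 × 3.42 + 1,360 × 2.63)/1,462 ≈ 2.69 years.

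*Assumptions (not in the documents):* inpatient share f, 5% to 30%; share q of ICD inpatients implanted in the same stay, 50% to 100%; later hospitalizations r, 0.5 to 1.5 per patient-year; negative binomial counts with dispersion 1.

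*Apparent ICD/OMT rate ratio* = (rT + f(1 − q)) / (rT + f).

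- f = 5%, q = 50%, r = 1.5: (4.03 + 0.025)/(4.03 + 0.05) = 0.99
- f = 10%, q = 100%, r = 1: 2.69/2.79 = 0.964
- f = 20%, q = 100%, r = 1: 2.69/2.89 = 0.931
- f = 30%, q = 100%, r = 0.5: 1.345/1.645 = 0.82

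*At least one stay,* with P0 = 1/(1 + rT) = 1/3.69 = 0.271, f = 10%, q = 100%, r = 1: OMT 1 − 0.271 × 0.9 = 75.6%, ICD 1 − 0.271 = 72.9%. The false-positive rate at nominal 5% is then about 22% for the chi-square test and 9% for the count model (normal approximation).

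*Total days,* assuming a mean of 12 further days, variance 12 + 12²/0.6 = 252, and q = 100%. The OMT:ICD ratio of means is (12 + df)/12, where d is the days remaining at randomization. False-positive rates come from 1,500 simulated trials per scenario:

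| f | d = 3: ratio, false-positive rate | d = 5: ratio, false-positive rate |
|---|---|---|
| 10% | 1.025, 6.6% | 1.042, 8.6% |
| 20% | 1.050, 10.3% | 1.083, 22.5% |
| 30% | 1.075, 19.3% | 1.125, 42.3% |

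If stays in progress are counted in both arms, or in neither, the rate ratio is 1.00 and this part of the problem disappears. Step 1 remains.

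**The case against.** A reader might infer that the plan counts an OMT inpatient's stay while erasing the same stay under ICD. The documents do not say so. Counting is tied only to the follow-up period, and if new admissions alone count, neither stay contributes. Protocol VI.B.4 also separates an index hospitalization from re-hospitalizations; the term is undefined and might cover an entry stay in either arm. This objection stands, and it makes the inpatient part conditional.

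A reader might also infer that many ICD inpatients will be implanted in the stay in which they were randomized. That is unsupported. Inpatients are permitted, but recruitment is mainly through clinics and mailings (Protocol VIII.A.1). Baseline is a clinic visit (III.F) with a six-minute walk test (VIII.B), participants must be stable on medical therapy (V.A), one week is a target, and SAP 2.2.4 expects some delay to implantation. The higher false-positive rates above therefore describe assumed scenarios and are not a forecast.

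Three further points are fair:

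- Protocol XIV.B.4 can be read to leave an illness admission countable even if an implant occurs during it. But it conflicts with VI.B.4, which defines the outcome, and SAP 1.3.2.4 is silent.
- Complications that prolong a stay remain serious adverse events, compared between arms (Protocol XV.C.5, SAP 2.2.9). They are not lost to the trial, but they are still missing from the hospitalization outcome.
- The outcome is exploratory (Protocol II.D and XV.C.4, SAP 1.2.4.2). Protocol III.A and the heading of SAP 1.3.2 place it among the secondary items, but no confirmatory claim rests on it.

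**Conclusion.** The concern holds in a limited form. The exclusion in Protocol VI.B.4 falls almost entirely on the ICD arm. As worded, it removes device-related hospital time (complication days, and infection stays that include a re-implantation) from an all-cause outcome, which favours the ICD. That rests on the text of VI.B.4 and on no assumption about stays in progress.

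A second bias in the same direction, from ICD inpatients' illness days, is possible but conditional: it requires that OMT inpatients' post-randomization days are counted and that the whole ICD stay is excluded. The plan settles neither.

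The size of both is unknown. The rate ratios of 0.99 to 0.82 apply only to the second bias, under the assumed shares and rates and that counting rule. All-cause mortality, quality of life and the co-morbidity interaction are unaffected. The point merits correction before analysis because the comparison is unblinded at site level, is tested at 0.05, and is cheap to put right.

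**What to change.** 1. **Anchor counting at randomization, identically in both arms.** For a stay in progress at randomization, either count its post-randomization days in both arms, or count only admissions that start after randomization in both arms. The first keeps complication days for ICD inpatients; the second is simpler but drops them within the entry stay. Do not start the clock at discharge: discharge follows randomization, the implant can delay it, and complication days before it would be lost.
2. **Narrow the exclusion** to the planned, uncomplicated implant or generator-change admission. Count stays or days due to a complication, device infection or other illness.
3. **Align** Protocol VI.B.4, Protocol XIV.B.4 and SAP 1.3.2.4, and define or remove the term index hospitalization.
4. **Add a sensitivity analysis** to SAP 2.2.7.2 that counts all post-randomization hospital days in both arms with no exclusion.

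Cost: a wording change in the protocol and SAP. Implantation and Hospitalization forms (Forms 12 and 19) already exist and total days are recorded; whether they carry admission, discharge and implant dates should be confirmed. Attributing days within an implant stay needs some judgement, so the rule should be written before outcome data are seen. The ICD arm's hospitalization figure may look slightly less favourable.
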